Prior to the date of surgery, all patients will have weight-bearing, long leg alignment radiographs. These will be taken using the technique described by Paley [25]. Pre-operative Hip Knee Ankle (HKA) angle, Medial Tibial Plateau Angle (MTPA) and Lateral Distal Femoral Angle (LDFA) will be measured for the operative knee using techniques described by Bellemans [11]. A pre-operative plan will then be formulated based on these measurements for re-creation of the coronal plane alignment within a predetermined 'safe zone'.

In order to define the kinematic alignment of each knee, we classified each patients' anatomy based on pre-disease alignment and the obliquity of their joint line using two frequently performed radiographic measurements. A pre-operative plan will then be formulated based on these measurements for re-creation of the coronal plane alignment within a predetermined 'safe zone'.

This 'safe zone' for this study is defined as 86 to 93 degrees for recreation of both the LDFA and the MPTA and -5 degrees to +4 degrees for the HKA. The authors set the parameters of the 'safe zone' centred on the means from Bellemans' paper describing the normal distribution of these angles [11] and also based on studies comparing analysis of alignment against survivorship by Parratte [26] and Ritter [27]. It was felt by the senior knee arthroplasty authors (SJM, DBC) that this safe zone would allow 72% of patients in the KA group to have their constitutional alignment restored according to the data from Bellemans et al., whilst minimising risk of significant component malalignment that would increase the risk of implant failure. It has also been the experience of our group that errors of up to 1 degree commonly occur in individual implant positioning with the use optical navigation. This could result in undesirable alignment errors of up to +/- 5 degrees for implant positioning, and up to +/- 6 degrees for HKA.

The pre-operative plan will involve defining the proximal tibial resection angle and distal femoral resection angles using the LDFA and MPTA measured from the pre-operative films. The resection angle will be set to the nearest whole degree if this falls within the range of 86 to 93 degrees. If it falls outside of this range then it will be set to

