either 86 to 93 degrees, depending on which end of the safe zone is closer. If the pre-operative plan requires LDFA and MPTA resections that would lead to a HKA greater than 4 degrees, then the LDFA and MPTA will be adjusted so the total HKA does not exceed the safe zone threshold. In order to reduce the risk of implant subsidence or loosening in the presence of osteoporotic bone, patients with a documented history of osteoporosis requiring bone anti-resorptive therapies, patients with documented insufficiency fractures or patients greater than 80 years of age will have the resection angle range for LDFA and MPTA narrowed to 87 to 93 degrees.

A web-based calculator has been designed to assist with these calculations to reduce any potential error. Most surgical instrumentation, including the navigation system used for this study, measure distal femoral and proximal cuts as either 'varus' or 'valgus'. For the LDFA, 90 degrees is neutral, 86 degrees is 4 degrees of valgus and 93 degrees represents 3 degrees of varus. To avoid errors at the time of surgery, it the varus/valgus figures that correspond to the surgical navigation data that are produced and recorded in the surgical plan. The final surgical plan will be recorded prior to randomisation.

Surgical Technique

Following randomisation, the patients will be allocated to either the intervention group or the control group. All procedures will be performed using optical navigation (OrthoMap Precision Navigation, Stryker, Kalamazoo, MI, USA). The distal femoral and proximal tibial resection will be made as per the allocated group. Femoral component rotation will be set in the KA group parallel to the native posterior condylar axis and in the MA group parallel to the surgical transepicondylar axis. In the KA group, if the planned tibial cut angle has been reduced in order to fall within the safe zone, then the femoral component will be externally rotated by the same amount that the tibial cut was reduced in order to rebalance the flexion gap. A secondary check of flexion gap symmetry will also be undertaken using a gap tensiometer.

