The surgeon will perform the initial bony resections using the same computer navigation system aiming for tibial and femoral component position perpendicular to the mechanical axis of the bone and an overall HKA of 0 degrees. These resections will be validated using the same computer navigation equipment to ensure maximum accuracy. The rest of the procedure will be completed as per the surgical technique described above.

OUTCOME MEASURES

Baseline Measures

Demographics

Baseline demographics will include age at time of surgery, gender, side of surgery, height, weight, body mass index, and primary diagnosis (osteoarthritis, rheumatoid arthritis, post-traumatic osteoarthritis).

Pre-operative Radiographic Data

Radiographic data to be recorded before surgery will include:

1. Hip-knee-ankle (HKA) angle. This is the angle subtended by the mechanical axis of the femur and mechanical axis of the tibia, with a negative value used for varus alignment and positive value for valgus alignment.
2. Lateral distal femoral angle (LDFA). This is the lateral angle subtended by the mechanical axis of the femur and a line across the distal femoral articular surface.
3. Medial proximal tibial angle (MPTA). This is the medial angle subtended by the mechanical axis of the tibia and a line across the proximal tibial articular surface.

Operative Data

Operative data to be recorded will include size of femoral component, size of tibial component, thickness of tibial bearing, size and type (oval, round onlay, inset) of patellar component, total operating time from wound incision to skin closure, intra-operative complications, VERASENSE™ data at 90, 45 and 10 degrees, and any soft tissue or bony adjustments made after the VERASENSE™ recordings.

In-Hospital Data

In-hospital data to be obtained will include total length of stay (from day of surgery to day of discharge), and discharge destination (home, in-patient rehabilitation unit, nursing home facility). Other data to be collected will include blood transfusion requirement (total number of units administered) and other in-hospital complications as specified in Table 2.

Primary Outcome Measure

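### The written hip-knee-ankle correction step names only the +4 degree limit, so the protocol's -5 degree varus limit is at best ambiguous and at worst left out (minor)

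*Protocol*

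**What the plan says.** All of this is in the Protocol.

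- **The zone.** Pre-operative Templating limits LDFA and MPTA to 86 to 93 degrees each, "and -5 degrees to +4 degrees for the HKA". It gives the aim as restoring native alignment while "minimising risk of significant component malalignment that would increase the risk of implant failure".
- **The intention.** The same section states twice: "A pre-operative plan will then be formulated based on these measurements for re-creation of the coronal plane alignment within a predetermined" safe zone.
- **The steps.** Each resection angle is set to the nearest whole degree inside 86 to 93, or to the nearer end of that range if it falls outside. Then comes the one HKA step: if the planned resections "would lead to a HKA greater than 4 degrees, then the LDFA and MPTA will be adjusted so the total HKA does not exceed" the safe-zone threshold. No step mentions -5 or varus.
- **The narrowed range.** Patients treated for osteoporosis, patients with insufficiency fractures and "patients greater than 80 years of age will have the resection angle range for LDFA and MPTA narrowed to 87 to 93 degrees". Their HKA zone is not changed.
- **The signs.** Pre-operative Radiographic Data defines HKA "with a negative value used for varus alignment and positive value for valgus alignment". For the femur: "For the LDFA, 90 degrees is neutral, 86 degrees is 4 degrees of valgus and 93 degrees represents 3 degrees of varus".
- **The tool.** A web-based calculator supports these calculations. Its HKA limits are not given.

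**The concern.** The zone has two ends and the step that enforces it names one. With varus negative, an HKA above 4 is a valgus knee. Someone who works through the steps literally would record a plan of 6 or 7 degrees varus unchanged. Someone who applies the zone would bring the same plan back to -5.

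The plan matters because in the kinematic alignment (KA) group the bone is cut to it, and the primary outcome, the pressure difference at 10 degrees of flexion, is read after those cuts and before any soft-tissue correction. If the HKA correction is taken on the tibia, the Surgical Technique section also has the femoral component externally rotated by the same amount. The zone is meant as protection against implant failure, and the section already calls HKA errors of up to 6 degrees undesirable after allowing for navigation error. The uncorrected plans start at that value or beyond it.

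**Working it through.** **Inputs.** LDFA and MPTA limits of 86 to 93 (or 87 to 93), whole degrees, HKA zone of -5 to +4, and a literal trigger of HKA > 4, all from Pre-operative Templating. The sign convention is from Pre-operative Radiographic Data.

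**Formula.** The Protocol does not write one, but its definitions imply it. The femur contributes 90 - LDFA: LDFA 86 gives +4 (valgus) and 93 gives -3 (varus), as the Protocol states. The tibia contributes MPTA - 90. Hence

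planned HKA = (90 - LDFA) + (MPTA - 90) = MPTA - LDFA.

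**Do the angle limits alone keep HKA inside the zone?** No. The extremes are 86 - 93 = -7 and 93 - 86 = +7.

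**Count of whole-degree plans (LDFA/MPTA).**

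| | 86 to 93 | 87 to 93 |
|---|---|---|
| All pairs | 8 x 8 = 64 | 7 x 7 = 49 |
| Above +4 | 6: 86/91, 87/92, 88/93 (+5); 86/92, 87/93 (+6); 86/93 (+7) | 3: 87/92, 88/93 (+5); 87/93 (+6) |
| Below -5 | 3: 92/86, 93/87 (-6); 93/86 (-7) | 1: 93/87 (-6) |
| Outside the zone | 9 | 4 |
| Caught by HKA > 4 | 6 | 3 |
| Missed | 3 | 1 |
| HKA range left after the literal step | -7 to +4 | -6 to +4 |

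The change needed to reach -5 is 1 degree for 92/86 and 93/87, and 2 degrees for 93/86.

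**Reading the 4 as a magnitude.** The trigger becomes HKA above +4 or below -4. It then also fires on plans at exactly -5 (91/86, 92/87, 93/88). But the sentence sets the safe-zone threshold as its target, and a plan at -5 does not exceed that, so no change follows. Plans at -6 and -7 move to -5, and plans at +5 to +7 move to +4. The result is -5 to +4, the stated zone.

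**With a two-sided trigger** (HKA < -5 or HKA > +4), the remaining range is -5 to +4 for both sets of angle limits, with no need to choose a reading.

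**The case against.** The strongest reply is that the two statements can be followed together. The zone is stated outright, the plan is twice said to be made within it, and nothing permits an HKA below -5. The step writes an unsigned 4 where the zone writes signed limits, so a magnitude reading is open and, as shown, reproduces the zone. All surgery is done by two surgeons, whom the Protocol credits with judging this zone, and a calculator assists them. Most of this stands. It means the text is not irreconcilable and that the missed plans are not intended. It does not make the step clear: under the Protocol's own sign convention the literal reading is the natural one, and the calculator's limits are not shown.

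A reader might infer three stronger things, none of which the documents support:

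- *That the Protocol plans knees at 7 degrees of varus.* The stated zone rules that out.
- *That the magnitude reading fails because it fires at -5.* It fires, but the target clause then requires no change.
- *That at most 28% of the KA group could be affected.* The Protocol says the surgeons felt that "this safe zone would allow 72% of patients in the KA group to have their constitutional alignment restored", and this rests on cited data describing the normal distribution of these angles. Trial patients have arthritic knees and are planned from their own films, so 100% - 72% = 28% is not a ceiling for them.

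**Conclusion.** The concern holds as a drafting fault in a safety-related planning rule. Read literally, the step omits the varus limit and leaves 3 of 64 possible plans (1 of 49 in the narrowed range) 1 to 2 degrees beyond it. Read generously, it is ambiguous.

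The counts assume planned HKA = MPTA - LDFA and a signed reading of the trigger. They count possible plans, not patients. The Protocol gives no distribution of these angles, so neither a patient share nor an upper bound can be stated. Only plans combining an LDFA of 92 or 93 with an MPTA of 86 or 87 are involved, so probably few KA knees are affected. Whether any is affected in practice depends on the calculator. Sample size, power and analysis do not change. Severity is minor.

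**What to change.** In Pre-operative Templating, change the trigger to: an HKA less than -5 degrees or greater than +4 degrees. The rest of the sentence can stay.

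Then confirm that the web calculator applies both limits. A short test is enough: LDFA/MPTA 93/86, 93/87 and 92/86 should be brought to -5, and 91/86, 92/87 and 93/88 should be left alone. With the 87 to 93 limits, 93/87 should be brought to -5.

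The cost is one clause and a few minutes of testing. A few varus knees may be planned 1 to 2 degrees further from their native alignment, which the stated zone already intends.

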Total knee arthroplasty (TKA) is a successful operation for treating pain and improving mobility in end-stage degenerative arthropathy. Despite advances in implant design and surgical technique, up to 20% of patients are less than satisfied, rating the outcome of their knee arthroplasty as fair or poor [1-3]. Outcomes registries such as the Arthroplasty Clinical Outcomes Registry (ACORN) in Australia [4] and the Swedish Knee Arthroplasty Register [5] report similar rates of dissatisfaction. The causes of this dissatisfaction are not clearly understood but are likely to be multifactorial, with surgical factors such as instability, malalignment, patellofemoral maltracking and stiffness regularly cited as potential contributors. [3, 5-8]

The traditional technique of achieving alignment in TKA is to resect the distal femoral and proximal tibial joint surfaces perpendicular to the long axis of each bone. This is termed the “mechanical alignment” method. External rotation of the femoral resections off the posterior aspect of the femur compensates for the loss of the normal varus alignment of the proximal tibia, leading to parallel cuts with the knee both in extension and flexion. The knee joint is parallel to the floor with the weight bearing axis of the lower limb passing through the middle of the knee joint. These conventional cuts have long been believed to create the best mechanical environment for the function and longevity of the prosthesis.

Advances over recent decades in fixation, manufacturing and improved wear characteristics of the bearing surfaces of total knee prostheses have led to a steady improvement in survivorship of the implants [9]. During this time, however, outcomes have remained consistent, with 15-20% of patients continuing to be dissatisfied with their joint replacement [1-3]. This satisfaction plateau has led some to question the need to focus on creating the ideal mechanical environment for the implant, and instead to suggest ways to accurately recreate the constitutional (or pre-arthritis) alignment of the knee, and thereby achieve improved patient outcomes [10].

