In 2012, Bellemans introduced the concept of ‘constitutional varus’ meaning that the proximal tibia is normally in a minor degree of varus alignment, not in neutral mechanical alignment (at right angles to the tibia and femur) and demonstrated the wide range of limb alignment in the normal population [11]. Subsequent to this, the “kinematic alignment” method was developed and first described by Howell et al. The aim of this method is to recreate the constitutional knee joint by recreating the movement around three axes that make up normal knee motion [12]: a transverse axis in the femur about which the tibia flexes and extends; a transverse axis in the femur about which the patella moves; and a longitudinal axis in the tibia about which the tibia internally and externally rotates on the femur. In order to achieve this, the bone

resections are made parallel to the surface of distal femur, posterior femur and proximal tibia, as opposed to perpendicular to the long axis of each bone. The theory is that a knee aligned to the patient's native anatomy will be better balanced (more stable throughout a range of movement), and therefore will require little if any adjustment of the soft tissue envelope to achieve normal knee motion [10].

Despite kinematic alignment gaining increasing traction amongst knee arthroplasty surgeons, there is a lack of clear evidence in the literature supporting claims that a kinematic alignment in total knee arthroplasty optimises knee ligament balance and hence improves patient outcomes.

The feasibility of achieving kinematic alignment with current prostheses and techniques that have been designed to achieve a neutral mechanical axis and a horizontal joint line is not clear. Furthermore, the term *kinematic* implies achievement of complex movement around three independent axes during normal gait. In the absence of dynamic, weight-bearing, 3-dimensional imaging, this intricate action is impossible to assess, and therefore accurate measurement is likely to be currently beyond our grasp. Lastly, the capacity to accurately determine the true joint lines once the arthritic process has occurred is yet to be determined.

New technology allows the surgeon to precisely quantify soft tissue balance in TKA on the operating table, throughout a range of motion [13]. Using these advances, there is evidence that a balanced TKA does, in fact, lead to improved patient outcomes [14].

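### The kinematic-arm rotation rule is not limited to reduced tibial varus; followed literally in a knee whose tibial valgus is cut back, it enlarges the flexion-gap asymmetry it is meant to remove

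*Protocol*

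**What the plan says.** The protocol's Pre-operative Templating section sets the safe zone at "86 to 93 degrees for recreation of both the LDFA and the MPTA and -5 degrees to +4 degrees for the HKA". A resection angle outside the range is set to "either 86 to 93 degrees, depending on which end of the safe zone is closer", so a tibia can be brought up to 86 degrees or down to 93. If the resulting HKA would be greater than 4 degrees, "then the LDFA and MPTA will be adjusted so the total HKA does not exceed the safe zone threshold". The Pre-operative Radiographic Data section reports HKA "with a negative value used for varus alignment and positive value for valgus alignment" and defines MPTA as a medial angle, so an MPTA above 90 degrees is tibial valgus.

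Under Surgical Technique, KA femoral rotation starts parallel to the native posterior condylar axis. An exception applies "if the planned tibial cut angle has been reduced in order to fall within the safe zone", with no mention of whether varus or valgus is meant. The action in that event is always the same: "then the femoral component will be externally rotated by the same amount that the tibial cut was reduced in order to rebalance the flexion gap". The next sentence adds a check of flexion-gap symmetry with a tensiometer but gives no action if the gap is asymmetric.

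The background states that external rotation of the femoral resections "compensates for the loss of the normal varus alignment of the proximal tibia".

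**The concern.** The rule gives one direction of rotation, external, for any reduction of the tibial cut. The zone it refers to reduces tibial cuts in both directions. By the protocol's own account, external rotation makes up for lost tibial varus. Where valgus is what has been reduced, the tibial cut already opens the medial side of the flexion gap, and external rotation opens the same side further. The instruction then defeats its stated aim of rebalancing the gap.

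This is an operative instruction for the intervention arm of a trial about knee balance. A surgeon who complies in such a knee adds asymmetry. One who rightly withholds the rotation departs from the written technique. The initial pressures at 45 and 90 degrees are compared between arms, and the optimal-balance definition uses 10, 45 and 90 degrees, so both are exposed.

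**Working it through.** The protocol gives no figure for this point, so there is none to reproduce. The check has three parts: sign, routes and frequency.

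**1. Sign.** Let asymmetry be the lateral minus the medial flexion gap in degrees, with the native knee at 0. Raising MPTA (less varus) opens the lateral side; lowering it (less valgus) opens the medial side. External rotation removes more posteromedial femur and opens the medial side. So

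asymmetry = (planned MPTA − native MPTA) − external rotation.

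| Native → planned MPTA | No added rotation | Under the rule |
|---|---|---|
| 84 → 86 (varus reduced) | +2 | +2 − 2 = 0 |
| 94 → 93 (valgus reduced) | −1 | −1 − 1 = −2 |
| 95 → 93 (valgus reduced) | −2 | −2 − 2 = −4 |

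The rule is right for varus. For valgus reduced by k, its size is 2k instead of k. In millimetres, using width × tan(angle) with an assumed 45 mm between compartment centres, k = 1 gives 45 × tan 2° = 1.6 mm under the rule and 45 × tan 1° = 0.8 mm without rotation. Over an assumed 40 to 50 mm the figures are 1.4–1.7 mm and 0.7–0.9 mm.

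**2. Routes to reduced valgus.**
- MPTA above 93 is set to 93.
- HKA above +4: with HKA taken as MPTA − LDFA (assumed), 6 of the 8 × 8 = 64 whole-degree plans in the zone exceed +4. As (MPTA, LDFA) they are (91,86), (92,86), (92,87), (93,86), (93,87) and (93,88), with excesses of 1, 2, 1, 3, 2 and 1 degrees. Taken wholly from the tibia, these leave MPTA at 90, 90, 91, 90, 91 and 92, never below 90. Any tibial share is therefore a reduction of valgus. In the narrowed 87–93 range, 3 of 49 plans exceed +4, all with MPTA 92 or 93. How the excess is split between femur and tibia is not stated, so this route counts only if the tibia takes part.

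**3. Frequency (assumed).** The protocol gives no MPTA distribution. It does say that about 72% of KA patients would have their alignment restored within the zone. The assumptions are normal angles, mean LDFA 87.5–89.5, mean MPTA 87–89.5 and not above mean LDFA, correlation 0 or 0.3, and a common SD solved to give 72% (1.18–2.47). A KA arm of up to 132/2 = 66 is used.
- The highest count is at mean MPTA 89.5 and SD 2.47: P(MPTA > 93) = 0.078, or 66 × 0.078 = 5.2 patients.
- Plans are in whole degrees, so a knee between 93.0 and 93.5 would be planned at 93 anyway. P(MPTA > 93.5) = P(Z > 4/2.47) = 0.053, or 66 × 0.053 = 3.5 patients.
- At mean MPTA 88.5 or lower, the count above 93 is at most 1.9, before allowing for rounding. The lower end of the range is 0.
- Size of k in the highest case: P(MPTA > 94) = 0.034, so 1 − 0.034/0.078 = 56% of knees above 93 have k of 1 degree or less. P(MPTA > 95) = 0.013, so k exceeds 2 in about 66 × 0.013 = 0.9 patients.
- HKA route, MPTA not above 93: probability at most 0.046, or 66 × 0.046 = 3.0 patients. This is an upper bound on exposure, not a count of wrong rotations.
- A wider SD of 3 at mean 89.5 would give P(MPTA > 93.5) = 0.091, or 6.0 patients. It does not fit the 72%: only about 76% of MPTA values alone would lie within 86–93, and about 57% of knees would have both angles inside if LDFA had the same mean and SD and were independent.

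**The case against.** The strongest defence is that the sentence is elliptical rather than wrong. The background says that "the proximal tibia is normally in a minor degree of varus alignment" and links external rotation to lost varus. A clause that names one direction of rotation and a rebalancing purpose reads naturally as covering reduced varus. Two surgeons perform every operation, which makes a literal misreading less likely. This stands as evidence of intent. It does not supply the missing word: the surgical plan is recorded in varus/valgus figures, and 5 degrees of valgus cut back to 3 is as much a reduction as varus is.

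It can also be said that the tensiometer check looks for exactly this asymmetry before the first sensor readings, and that sensor-guided balancing follows. The check may well catch the problem in theatre, but no action is attached to it. Final balancing comes after the initial pressures have been recorded, so it cannot protect those readings.

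The points about size stand in full. The HKA route is conditional, rounding removes the smallest cases, and a typical k of 1 degree equals the positioning error that the protocol calls common.

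A reader might go further and infer that the primary comparison is biased, or that KA could be shown falsely superior. The documents do not support that. The primary outcome is the pressure difference at 10 degrees, while femoral rotation acts mainly in flexion, and the extra asymmetry falls on the KA arm. Nor do they support the inference that the surgeons intend to rotate valgus knees the wrong way.

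**Conclusion.** The point holds as a minor error of wording in an operative rule. As written, the rule covers knees in which tibial valgus is cut back, and there it gives the wrong direction. The sign result rests on simple geometry and on the protocol's own statement of what external rotation is for. The counts rest on assumed distributions fitted to one figure in the protocol: none to about 3 or 4 of 66 KA patients by the MPTA route, plus from none to about 3 exposed by the HKA route, fewer if the femur takes the adjustment. Most would have k near 1 degree. The consequence is confined to initial pressures at 45 and 90 degrees and the optimal-balance outcome in a few KA knees. Confidence is medium, because a varus-only intent is likely.

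**What to change.** In the Surgical Technique section, make the trigger a reduction in the varus of the planned tibial cut, made to bring it into the safe zone. Add one sentence: where tibial valgus is reduced, by the MPTA or the HKA limit, no external rotation is added and the femoral component stays parallel to the native posterior condylar axis. Whether to rotate internally by k instead, which would bring the asymmetry to 0 in the geometry above, is for the surgeons to decide; either way, the direction should be written.

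The cost is one clause and one sentence, with no extra patients, visits or procedures. No new recording is needed, since the varus/valgus plan made before randomisation and the pre-operative MPTA already show the direction of the change. The downside is that, with no rotation, k degrees of asymmetry remain in valgus-reduced knees, to be dealt with at the tensiometer check and final balancing.
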